### 6.3 Visit 2 (Day of Procedure)

Patients will be undergoing surgical scar excision using local or general anesthesia depending on the size of scarring and surgeon preference for excision. [name] and/or his surgical staff will perform the surgical scar excision. Patients will receive their first 2 weeks of study drug with de-identified treatment agents to be applied either distal or proximal region of surgical site.

### 6.4 Phone Interview #1 (Week 0, Day 1 postop)

Patients will be contacted at 24 hours following scar excision. Any adverse effects present will be assessed and noted. Measures to address these effects will be taken on a per-patient basis.

### 6.5 Phone Interview #2 (Week 1 postop)

Patients will be contacted 1 week following scar excision. Any adverse effects present will be assessed and noted. Measures to address these effects will be taken on a per-patient basis.

## **6.6 Visit 3 (Week 2 postop)**

The scar will be photographed and quality questionnaires (VSS and POSAS) will be filled out. Patients will receive their third and fourth week of study drug with de-identified treatment agents to be applied either distal or proximal region of surgical site. Post-operative ultrasound and/or 3D imaging will be performed to assess scar height. Post-operative safety testing with laboratory studies (including hepatic and renal function, complete blood count with differential, blood glucose level and calcium) and cardiac monitoring (ECG) will be performed. Additional safety evaluation including clinical exam with local safety evaluation to assess tolerability (e.g. erythema, edema, vesicle formation, necrosis, ulceration etc.) and neuropsychiatric adverse event assessment will be completed.

## **6.7 Phone Interview #3 (Week 3 postop)**

Patients will be contacted 3 weeks following scar excision. Any adverse effects present will be assessed and noted. Measures to address these effects will be taken on a per-patient basis.

## **6.8 Visit 4(Week 4 postop)**

The scar will be photographed and quality questionnaires (VSS and POSAS) will be filled out. Post-operative ultrasound and/or 3D imaging will be performed to assess scar height. This visit will include two 5-mm skin punch biopsy (one from distal site and one from proximal scar site) performed under local anesthesia in a dedicated procedure room. This sample will be processed by the study staff for histological/molecular evaluation to analyze scar characteristics. Post-treatment safety testing with laboratory studies (including hepatic and renal function, complete blood count with differential, blood glucose level and calcium) and cardiac monitoring (ECG) will be performed. Additional safety evaluation including clinical exam with local safety evaluation to assess tolerability (e.g. erythema, edema, vesicle formation, necrosis, ulceration etc.) and neuropsychiatric adverse event assessment will be completed.

Follow-up visits may be scheduled per patient request.

## **6.9 Phone Interview #4: (Month 2 post op)**

Patients will be contacted 2 months following scar excision. Any adverse effects present will be assessed and noted. Measures to address these effects will be taken on a per-patient basis.

## **6.10 Visit #5: (Month 3 post op)**

The scar will be photographed and quality questionnaires (VSS and POSAS) will be completed. Patients will be assessed for any adverse events.

Range for phone interviews for call 2 and 3: +/- 1 day

Range for phone interview for call 4: +/- 1 week

Range for study visits 3 and 4: +/- 1-3 days

Range for study visit 5: +/- 2 weeks

## 6.11 Schedule of Events

Study Activity	Schedule of Events									
	Visit 0 Pre-op	Visit 1 Pre-op	Visit 2, Week 0, Day 0 Surgery	Phone 1, Week 0, Day 1	Phone 2 Week 1	Visit 3, Week 2	Phone 3 Week 3	Visit 4, Week 4	Phone 4, Month 2	Visit 5 Month 3
Informed consent	X									
Randomization		X								
General evaluation, physical exam and vital signs a		X								
Scar photography		X	X			X		X		X
Neuropsychiatric exam and local safety evaluation (baseline and adverse event assessment) b		X				X		X		
Laboratory studies c		X				X		X		
Quality questionnaires (VSS and POSAS) d		X				X		X		X
US and/or 3D imaging e		X				X		X		
Cardiac monitoring (ECG) f		X				X		X		
Treatment application patient education		X								
Dispense study drug g			X			X				
Surgical scar excision			X							
5-mm skin punch biopsy		X						X		
Phone interview				X	X		X		X	
Adverse event evaluation				X	X	X	X	X	X	X

a: Vital signs include blood pressure, pulse, temperature and respiratory rate. Physical exam includes skin check.  
b: Clinical exam for neuropsychiatric exam will include evaluation for confusion and hallucination.  
c: Hepatic and renal function, complete blood count with differential, blood glucose level and calcium  
d: Quality questionnaires: Vancouver Scar Scale (VSS) and Patient Observer Scar Assessment Scale (POSAS).  
e: Ultrasound (US) and/or 3D-scanner imaging used to evaluate scar height.  
f: Safety evaluation will include cardiac monitoring with electrocardiogram (ECG).  
g: Single dose containers with de-identified treatment agents (active topical drug and silicone-base only).

## 7 Statistical Plan

### 7.1 Sample Size Determination

This is a first in-human exploratory study to determine the efficacy of topical pentamidine. There will be 80% power to detect an effect size of 1.3 standard deviations for the comparison of MED between any two treatment groups. This calculation is based a two-sided unpaired t-test with a type I error of 0.05.

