## 2 Study Objectives

The primary goal of this randomized clinical trial will be to directly evaluate safety of topical scar prevention product and placebo base control in patients with hypertrophic scarring. Patients with known diagnosis of hypertrophic scar will be enrolled. Secondarily, we will evaluate initial signs of treatment efficacy using topical product.

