## 3 Study Design

### 3.1 General Description

This study is a double-blind pilot study of scar excision procedure followed by treatment with either TP in PCCA PP versus PCCA PP silicone base only. Current management for patients with hypertrophic scar includes silicone-based treatment. At our institution we treat patients with scar excision surgery without topical scar cream following the procedure. However, a significant proportion of patients continue to fail this treatment modality leading to scar recurrence. Indeed, individual patient response to therapy varies based on patient characteristics including ethnicity. As such, we plan to treat the same patient with both TP in PCCA PP and PCCA PP alone at different ends of their scar. In this way, we can better determine efficacy of these topical agents in biologically controlled setting with reduced response variability. We plan to enroll patients with minimum hypertrophic scar length  $\geq 3$  cm.

Those patients who successfully qualify based on inclusion and exclusion criteria will be invited to participate in the trial. Following informed consent, eligible subjects will undergo pre-operative tests to include blood work and EKG. Preoperative photographs of the scar site will be taken. Scar quality questionnaires (VSS and POSAS) will be completed and a scar ultrasound performed.. A 5-mm skin punch biopsy will be obtained from the lateral edge of the scar at both the proximal and distal ends of the scars, under local anesthesia. Alternatively, the first punch biopsy may occur prior to the surgical procedure while the patient is under anesthesia. Part of the sample will be stored in formalin and prepared for histological staining. The other portion will be frozen and prepared for molecular analysis. All participants will receive both treatments to be applied either at the proximal end or the distal end of the scar. Treatment application will be randomized. For example, topical agent A will be applied to the proximal end of the scar and will contain either TP

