### 3.2 Number of Subjects

Ten subjects will be enrolled in this trial.

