### 7.2 Statistical Methods

#### Primary Hypothesis

This primary hypothesis will be evaluated by paired t-test.

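### The power statement in Section 7.1 describes an unpaired comparison of an undefined outcome, not this trial of 10 within-patient pairs, and Section 7.2 does not match the Study Summary

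*Combined protocol and SAP*

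**What the plan says.** **Sample size.** Section 7.1 opens with "This is a first in-human exploratory study to determine the efficacy of topical pentamidine". It then states "There will be 80% power to detect an effect size of 1.3 standard deviations for the comparison of MED between any two treatment groups" and adds "This calculation is based a two-sided unpaired t-test with a type I error of 0.05". It gives no number per group and does not say which standard deviation the 1.3 refers to.

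**Design.** Section 3.2 says "Ten subjects will be enrolled in this trial". Section 3.1 says "we plan to treat the same patient with both TP in PCCA PP and PCCA PP alone at different ends of their scar", and gives as the reason that efficacy can then be judged "in biologically controlled setting with reduced response variability".

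**Purpose.** Section 2 says "The primary goal of this randomized clinical trial will be to directly evaluate safety of topical scar prevention product and placebo base control". Efficacy is secondary there, in the Study Summary and in Section 3.5. The primary endpoint in Section 3.4 is the type and number of serious adverse events.

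**Analysis.** Apart from its headings, Section 7.2 is one sentence: "This primary hypothesis will be evaluated by paired t-test". No hypothesis comes before it. The Statistical Methodology row of the Study Summary is fuller. Its primary analysis describes adverse events. Its secondary analysis compares change in lesion height and characteristics by paired t-test or Wilcoxon signed rank test. It assigns VSS and POSAS to a two-factor ANOVA with repeated measures on both factors.

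**MED.** The term is not in the List of Abbreviations, the endpoints (3.4, 3.5), the source data list (3.6) or the Schedule of Events (6.11). Its only other appearance is under Data Quality Assurance in Section 9.3, where MED data are to be checked against skin images. It is not defined there either.

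**The concern.** The plan's one power statement fits neither the design, nor the planned test, nor any listed outcome. An unpaired calculation assumes two independent sets of patients and has no place for the correlation between the two ends of one scar, although that correlation is the stated reason for the design. A reader therefore cannot learn from Section 7.1 what difference 10 pairs can detect, or in which measure.

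Section 7.2 adds a second difficulty. Taken alone, it would have an analyst run a paired t-test as the primary analysis of an unnamed outcome. The Study Summary reserves that test for the secondary analysis. Section 7.2 also omits the descriptive adverse-event analysis, the Wilcoxon option and the repeated-measures ANOVA.

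**Working it through.** **Inputs.** From Section 7.1: effect 1.3 SD, two-sided alpha 0.05, 80% power, unpaired t-test. From Section 3.2: 10 patients. From Section 3.1: both products in every patient, hence 10 pairs. The documents give no within-patient correlation (rho), so every rho below is an assumption.

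**1. Reproducing the stated 80%.** Assume n = 10 per group, since Section 7.1 gives no n. For a two-sample t-test, df = 2n − 2 = 18 and the noncentrality is d × √(n/2) = 1.3 × √5 = 2.907.

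| Calculation | Result |
|---|---|
| Exact noncentral t, 10 per group | power 78.5% |
| Exact, 11 per group | power 82.6% |
| Exact, 10 per group, difference detectable with 80% power | 1.32 SD |
| Normal approximation, n per group = 2 × (1.96 + 0.84)² / 1.3² = 9.3 | 10 per group |
| Exact, 5 per group (10 patients split in two) | power 44.0% |

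The stated figure is therefore about what two independent groups of 10, or 20 patients, would give.

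**2. The same question for pairs.** For a paired t-test, df = n − 1 and the noncentrality is dz × √n, where dz is the mean difference divided by the SD of the within-patient differences. Solving for 80% power at two-sided 5%:

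| Pairs analysed | Detectable dz |
|---|---|
| 10 | 0.996, i.e. 1.00 |
| 9 | 1.067, i.e. 1.07 |
| 8 | 1.156, i.e. 1.16 |

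The smaller counts are shown because Section 7.3 restricts the analysis to patients who complete everything and Section 4.4.1 does not replace a single withdrawal.

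**3. If 1.3 is in single-site SDs.** With equal SDs at the two ends, dz = 1.3 / √(2(1 − rho)). With 10 pairs:

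| Assumed rho | dz | Power at 1.3 single-site SDs | Single-site SDs detectable with 80% power, 0.996 × √(2(1 − rho)) |
|---|---|---|---|
| 0 | 0.919 | 73.5% | 1.41 |
| 0.15 | 0.997 | 80% | 1.30 |
| 0.25 | 1.061 | 84.7% | 1.22 |
| 0.5 | 1.300 | 95.4% | 1.00 |

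At rho = 0 the noncentrality is 0.919 × √10 = 2.907, the same as in step 1. Power falls from 78.5% to 73.5% only because the paired test has 9 degrees of freedom instead of 18. From rho of about 0.15 upward, the paired test has at least the stated 80%.

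**4. If 1.3 is in SDs of the differences.** Power with 10 pairs is 95.4%, and a simulation of 200,000 trials also gave 95.4%.

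**5. Section 7.2 beside the other sections.** The Study Summary, Section 2 and Section 3.4 all make safety primary. Section 7.2 is the only place that attaches a significance test to something called primary, and it does not say what is tested.

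**The case against.** The strongest reply is that little turns on this. It is an exploratory safety pilot. Every planned between-product test of efficacy already respects the pairing, so no result would be computed wrongly because of Section 7.1. If 10 per group was intended, the arithmetic is close to right. Under the positive correlation that Section 3.1 expects, the unpaired figure errs on the cautious side. All of that stands, and it limits the weight of the point. It does not supply an outcome for the power statement, a hypothesis for Section 7.2 or a match between the two sections on analysis. The protocol chose to claim 80% power, so the claim should describe its own design.

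Three stronger readings are tempting, and the documents do not support them.

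- A reader might infer that the trial is underpowered. With 10 pairs, power at 1.3 single-site SDs falls below the stated 80% only if the correlation is under about 0.15, and the documents give no correlation.
- A reader might infer that the protocol leaves open whether safety or efficacy is primary. Three other places agree on safety. Section 7.2 is the outlier, and the efficacy wording in Section 7.1 sits beside the word exploratory, so it is loose drafting more than a rival objective.
- A reader might infer that MED is stray text to be struck out. The documents do not show whether it is that or a measure the sponsor meant to include.

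**Conclusion.** Wrong as written, with limited harm. Section 7.1 uses a test that the design rules out and an outcome that the protocol never defines. Section 7.2 names a test for an unstated hypothesis and departs from the Study Summary.

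The usable statement for this design is 80% power at 1.00 SD of the within-patient differences with 10 analysed patients, rising to 1.16 with 8. It rests on approximately normal differences and a two-sided 5% paired t-test, and needs no assumed correlation. Any translation into single-site SDs does need one, and the 73.5% to 95.4% range covers only assumed values from 0 to 0.5. The calling of the unpaired figure conservative holds under moderate positive correlation, not in general.

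**What to change.** 1. **Restate Section 7.1 for pairs.** Suggested text: *The primary objective is safety, analysed descriptively. For [one named secondary outcome and time point, measured at both scar ends], a two-sided 5% paired t-test has 80% power to detect a mean difference of 1.00 SD of the within-patient differences with 10 analysed patients (1.07 with 9, 1.16 with 8).* The sponsor should name the outcome and time point. In doing so it should reconcile the Study Summary, which uses change in lesion height, with Section 3.5, which compares lesion volume before surgery with weeks 2 and 4.

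2. **Resolve MED.** In Section 7.1, replace it with the outcome named above. In Section 9.3, replace or define it, and keep the cross-check against images.

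3. **Align Section 7.2 with the Study Summary.** Primary: adverse events are described. Secondary: change in lesion height and characteristics is compared between scar ends by paired t-test or Wilcoxon signed rank test, and VSS and POSAS are analysed by two-factor ANOVA with repeated measures on treatment and follow-up time.

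**Cost:** rewording of Sections 7.1, 7.2 and 9.3. No patients, visits or procedures are added.

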### 7.2 Statistical Methods

#### Primary Hypothesis

This primary hypothesis will be evaluated by paired t-test.

### 7.3 Subject Population(s) for Analysis

This study will include only subjects who completed ALL study-related procedures and follow up.

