**Study Summary**

Title	Double Blind, Single-Center, Randomized, Within-Subject Placebo, Phase I Study Evaluating the Effects of Topical Pentamidine in Prevention of Hypertrophic Scar Formation
Running Title	Novel Topical Gel for Hypertrophic Scar Prevention
IRB Protocol Number	17-005230
Phase	Pilot Study
Methodology	Double Blind, Single-Center, Randomized, Within-Subject Placebo Phase I Study
Overall Study Duration	3 months
Subject Participation Duration	3 months
Single or Multi-Site	Single site
Objectives	Evaluate safety of topical pentamidine (TP) as an adjuvant to surgical scar excision (SSE) in the treatment of hypertrophic scar formation. Safety will be measured by serial monitoring for adverse events following the procedure and during treatment duration. Secondarily, study will evaluate drug quality and standardizations as well as investigate initial signs of efficacy.
Number of Subjects	10
Diagnosis and Main Inclusion Criteria	Hypertrophic scar diagnosed in Mayo Clinic Department of Dermatology or Division of Plastic Surgery, Rochester, Minnesota.
Study Product, Dose, Route, Regimen	Pentamidine, delivered as topical formulation containing 2% TP in silicone-containing base, PCCA Pracasil™-Plus (PP), versus placebo base alone. Approximately 1.8 mL of product in allotted single dose containers will be applied every 48 hours for 4 weeks following surgical scar excision.
Duration of Administration	Once every 48 hours for 4 weeks.
Reference therapy	SSE with silicone compounding base only (PCCA PP).
Statistical Methodology	The primary analysis will use descriptive statistics to document adverse events between treated and untreated lesions. The secondary analysis will use paired t-test or Wilcoxon signed rank test to compare the change in lesion height and characteristics between the treated and placebo groups following SSE (TP + PCCA PP vs. PCCA PP alone). In addition, two-factor analysis of variance (ANOVA) with repeated measures on both factors will be used to evaluate the effect of treatment and follow-up time for other continuous measures such as Vancouver Scar Scale (VSS) and Patient and Observer Scar Assessment Scale (POSAS).

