### 3.4 Primary Study Endpoints

**Aim #1:** Identify the type and number of serious adverse events related to TP in PCCA PP compared to PCCA PP base alone following surgical scar excision. While we do not anticipate any severe adverse events, we will monitor for the following:

- Skin infection
- Skin irritation
- Wound dehiscence
- Clinically significant abnormalities in physical examination and vital signs.

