#### **4.4 Early Withdrawal of Subjects**

##### **4.4.1 When and How to Withdraw Subjects**

Subjects may withdraw from the study for any of the following reasons: safety issues, inability or unwillingness to adhere to protocol requirements, or if the subject desires to withdraw from the study. A single subject withdrawn from the study will not be replaced. If two or more patients have withdrawn (with the exception of safety reasons) one of the subjects will be replaced with a new enrollee. The decision to withdraw subjects and the responses below will occur under the following circumstances.

- Patients wishing to withdraw from the study: Patients wishing to withdraw from the study should provide written indication of these wishes.
- Patients unable or uncooperative to continue in the study: If possible, patients should be contacted in an attempt to determine the reasons for the inability to complete the study. After at least three attempts and failure to complete required testing the patient will be considered out of the study.
- Withdrawn from study due to safety reasons: See section below for the response to drug related adverse events and patient withdrawal from the study. Generally, even patients with a drug related adverse event will continue with the test schedule as the test schedule includes minimal risk tests and is used to monitor and gauge continued long term effects of the treatment.

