##### **4.4.2 Data Collection and Follow-up for Withdrawn Subjects**

The sponsor of the study is responsible for following up on patients who develop adverse reactions to treatment. All study participants will undergo risk-appropriate follow-up until study-related adverse events have been fully treated and resolved.

[figure not shown]

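### The only analysis population is full completers, so a patient who dies or withdraws for safety drops out of the primary adverse event summary

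*Combined protocol and SAP*

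**What the plan says.** Section 7.3, the section on analysis populations, is one sentence: "This study will include only subjects who completed ALL study-related procedures and follow up". It does not separate safety from efficacy. No safety, as-treated or all-randomised set appears anywhere else.

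The primary purpose is safety throughout:

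- Section 2: "The primary goal of this randomized clinical trial will be to directly evaluate safety of topical scar prevention product".
- Section 3.4, the primary endpoint: "Identify the type and number of serious adverse events related to TP in PCCA PP compared to PCCA PP base alone".
- Study Summary, Statistical Methodology: "The primary analysis will use descriptive statistics to document adverse events between treated and untreated lesions".
- Section 8.4 gives safety, along with preliminary efficacy, as the purpose of the end-of-study analysis.

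The plan also foresees patients who will not complete. Section 4.4.1 says "Subjects may withdraw from the study for any of the following reasons: safety issues" and then lists other reasons. Section 8.5 names a death related to the agent as a trigger for suspending accrual. On replacement, Section 4.4.1 says "A single subject withdrawn from the study will not be replaced"; after two or more withdrawals one subject is replaced, with an exception for safety withdrawals.

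**The concern.** Under Section 7.3 as written, the primary outcome can itself decide who is analysed. A patient who dies before Month 3, or who leaves because of a reaction, has not completed every procedure and all follow-up. That patient therefore falls outside the only defined population, and the event falls outside the primary summary.

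The direction of the error depends on who leaves. If patients with events leave more often than patients without, the completer summary understates harm. If event-free patients leave more often, it overstates the proportion affected. If both leave at the same rate, the expected proportion is unchanged.

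Two features make this serious here. There are only 10 patients, so one exclusion can decide whether any related event is shown. And each patient carries both products, so dropping a patient removes both scar ends: a local reaction on one side also leaves the within-patient comparison.

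**Working it through.** **Reading the sections together.** Sections 2 and 3.4 and the Study Summary make adverse events the primary objective, endpoint and analysis. Section 7.3 limits the analysis to completers. Sections 4.4.1 and 8.5 foresee non-completion caused by adverse events. Sections 4.4.2, 8.2, 8.3, 8.5 and 8.6 require events to be followed, recorded, reported and monitored, but none says that the patients concerned enter the analysis.

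**Inputs.** Ten patients, each receiving both products (Sections 3.1 and 3.2). The plan gives no event rate and no withdrawal rate, so there is no figure of its own to reproduce on this point. All rates below are assumptions, shown over a range.

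**Step 1: one patient** (exact Clopper-Pearson 95% limits).

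- True result, one affected patient among 10 treated: 1/10 = 10% (0.3 to 44.5%).
- The affected patient withdraws: 0/9 = 0%, upper limit 1 − 0.025^(1/9) = 33.6%.
- The affected patient stays and one event-free patient withdraws: 1/9 = 11.1% (0.3 to 48.2%).

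**Step 2: chance that the summary shows no event.** Let p be the event risk per patient and w the share of affected patients who withdraw, with no other withdrawals. A safety set shows none with probability (1 − p)^10. A completer set shows none with probability (1 − p(1 − w))^10, because an event is visible only if the patient also completes. For example, at p = 0.20 and w = 0.10 this is 0.82^10 = 13.7%, against 0.80^10 = 10.7%.

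| Event risk p | Safety set | Completers, w = 10% | w = 25% | w = 50% | w = 75% |
|---|---|---|---|---|---|
| 20% | 10.7% | 13.7% | 19.7% | 34.9% | 59.9% |
| 10% | 34.9% | 38.9% | 45.9% | 59.9% | 77.6% |
| 2% | 81.7% | 83.4% | 86.0% | 90.4% | 95.1% |

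At w = 10% the increase is 1.7 points (p = 2%), 4.1 points (p = 10%, from unrounded values) or 3.0 points (p = 20%). The 2% row is closest to a rare serious event, which is what Section 3.4 counts.

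**Step 3: direction of the bias.** Let d be the share of event-free patients who withdraw. The expected proportion among completers is p(1 − w) / [p(1 − w) + (1 − p)(1 − d)]. With p = 0.20:

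- w = 0.10, d = 0: 0.18/0.98 = 18.4%
- w = 0.10, d = 0.10: 0.18/0.90 = 20.0%
- w = 0, d = 0.10: 0.20/0.92 = 21.7%

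The bias is downward only when w exceeds d.

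**Step 4: how often the rule would apply.** If each patient fails to complete, for any reason, with probability 5%, 10% or 20%, the chance of at least one non-completer among 10 is 1 − 0.95^10 = 40%, 1 − 0.90^10 = 65% or 1 − 0.80^10 = 89%.

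**The case against.** The strongest reply is that Section 7.3 was meant for efficacy only. Section 7.1 speaks of efficacy, Section 7.2 names a paired t-test, and the adverse event analysis is described in the Study Summary without any completer condition. The reading is possible, but it is stated nowhere. If it is the intended one, the primary analysis has no defined population at all, and the same correction is needed.

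The second reply is that no safety data are lost. This stands. Section 8.2 requires every adverse event to be recorded, the Section 8.5 rules and Section 8.6 monitoring still apply, and Section 4.4.2 says "All study participants will undergo risk-appropriate follow-up until study-related adverse events have been fully treated and resolved". The defect affects the analysis and its report, not surveillance during the trial.

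The third reply is that few affected patients would leave. Section 4.4.1 says "Generally, even patients with a drug related adverse event will continue with the test schedule", and Section 8.5 keeps patients in follow-up when dosing is stopped. This also stands in large part: it makes the low withdrawal shares in the table the more plausible ones, and there the effect is small. It is not complete protection, however. The wording in Section 4.4.1 is general and allows exceptions, and a patient who dies cannot continue. The plan also does not say whether a patient whose dosing was stopped, or whose Month 3 visit became the permitted phone interview, still counts as having completed everything.

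**Conclusion.** The concern holds, and the plan needs correcting on this point. Applied as written, Section 7.3 can give a wrong primary safety result, and nothing elsewhere in the documents prevents it.

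The conclusion rests on the text, not on any assumed rate. The likely average distortion is modest: a few percentage points in the chance of showing no event if about one affected patient in ten leaves. It is large only if half or more leave, and its direction depends on who leaves. The stronger reason to correct it is the individual case. In a study of 10, a single death or safety withdrawal could turn 1/10 into 0/9 in the primary summary.

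**What to change.** In Section 7.3, define a safety set of every patient who receives at least one application of either product. State that the primary adverse event analysis uses this set whether or not dosing or follow-up is completed, and repeat this in the Study Summary. If a completer set is kept, restrict it to efficacy, and state whether stopped dosing or a Month 3 phone interview counts as completion. Which population leads the efficacy analysis is a separate decision and need not delay this change.

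It would also help, though it is not essential to the correction, to summarise local events by the product applied at each site and systemic events (laboratory, ECG, neuropsychiatric) per patient, since a systemic event cannot be assigned to one end of the scar.

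The cost of the safety set is wording in two places. It uses data that Section 8.2 already requires and needs no extra patients, no extra visits and no change to the descriptive method.
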